3.2 Primary Study Endpoints

To observe a reduction or elimination of symptoms caused by gadolinium deposition after administration of a GBCA.

3.3 Secondary Study Endpoints

To observe increased elimination of gadolinium in 24-hour urine collections post infusion therapy, estimated at greater than two-fold increase.

The pre-chelation Gd amount in urine should decrease from the first to third treatment.

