3.1 General Design

This is an open-label study. Patients will be evaluated at a baseline visit to determine eligibility and obtain informed consent before proceeding on to study-related procedures. Most patients coming for treatment will have had prior gadolinium testing greater than 30 days post MRI/contrast agent that shows an elevated result, thus eligibility for chelation therapy.

In addition to previous gadolinium testing, subjects will be instructed to perform a 24-hour urine collection (at visit 0) to determine a baseline for evaluating the elimination of gadolinium before initiating the first treatment.

At the first and subsequent chelation therapy visits, a baseline blood pressure will be obtained, an IV will be placed by Vascular Interventional Radiology (VIR) nursing staff, and 1L of normal saline will be connected. Initially, 2.5 mL of Ca-DTPA (1 g/5 mL) will be administered over a period of 1 minute. Five (5)

minutes post DTPA blood pressure will be collected again. The saline will then be administered at a rate of 300 mL/hr over 30 minutes with the patient seated and with hands lowered by their sides to allow the chelator to dwell slightly in the soft tissues of the hands and feet. The patient will then be positioned in a supine position on a hospital bed/gurney and the infusion rate will then be increased to 750 mL/hr over the next 60 minutes. With 10 minutes remaining (80 minutes after the start of infusion), the remaining 2.5 mL of Ca-DTPA will be administered I.V. over a period of 1 minute. The infusion of saline will continue another 9 minutes, and the I.V. line will then be removed. The patient will be instructed to drink plenty of fluids that evening. The following day, the treatment will be repeated using Zn-DTPA.

The patient will be instructed to collect 24-hour total urine samples beginning once chelation therapy starts, and bring back to the lab the following days.

The process will be repeated monthly, for a total of 3 chelation treatment time-points.

Patients will come to clinic for follow up to be assessed for adverse events one week following each treatment. Patients will be asked to fill out pain/QOL questionnaires and given a brief physical exam. Patients who live greater than 3 hours away will be assessed via phone call and instructed to get labs drawn locally. Patients may be advised to seek medical attention if the investigator feels any adverse reaction is not expected or is severe.

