4.3 Subject Recruitment and Screening

Study subjects will be recruited as they seek us out from patient activist groups of gadolinium toxicity. In most cases it will be a first come first serve basis, but patients will also be prioritized based on levels of incapacitation by the gadolinium deposition disease.

Screening will include:

- 24-hour gadolinium urine
- Pain/QOL assessments
- Blood chemistries: calcium, zinc, manganese, magnesium, sodium, potassium, chloride, Creatinine, BUN, CO₂, Phosphorus, CBC/Diff, urinalysis, creatinine clearance.

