5.9.4 Return or Destruction of Study Drug

At the completion of the study, there will be a final reconciliation of drug shipped, drug consumed, and drug remaining. This reconciliation will be logged on the drug reconciliation form, signed and dated. Any discrepancies noted will be investigated, resolved, and documented prior to return or destruction of unused study drug. Drug destroyed on site will be documented in the study files.

6 Study Procedures

6.1 **Visit 0-** The patient will be seen and evaluated by a UNC clinician regarding symptoms, assessments, a physical exam, a medication history and lab values up to one week prior to anticipated therapy start date. After agreeing to participate in the study, a coordinator will obtain informed consent signatures and the patient will be instructed to collect a 24-hour urine so that gadolinium can be measured for pre-treatment values.

6.2 **Visit 1-** The patient will come for infusion chelation therapy with Ca-DTPA to be done in the Clinical and Translational Research Center. Patient will void and have a baseline blood pressure taken before start of treatment. A urine pregnancy test will be performed if the subject is a woman of child-bearing potential. Blood samples will be collected by phlebotomy trained staff at the Clinical & Translational Research Center (CTRC) at UNC Memorial hospital. Patient blood samples will be obtained just prior to intravenous administration of Ca-DTPA or Zn-DTPA. The IV will be placed by nursing staff, and the infusion of normal saline will begin. The first injection of Ca-DTPA is performed by the investigator, or one of the co-investigators. Five (5) minutes post injection of Ca-DTPA another blood

pressure will be taken. Saline will continue for another 80 minutes, and the second injection of Ca-DTPA will be given by an investigator, followed by the last 10 minutes of saline infusion. IV will be discontinued, vitals checked, and patient will be discharged home. Patient will begin 24-hour urine collection once the infusion is started. They will be instructed to drink plenty of fluids. Analog pain scale sheets will be given to the subject to fill out starting with day 1 through day 6 post treatment, which will be returned on the day 7 visit. Urine is to be brought in on 2nd day of therapy.

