6.3 **Visit 2-** The patient subject will come for the second infusion therapy with Zn-DTPA. Patient will void and have a baseline blood pressure taken prior to initiation of therapy. Blood samples will be collected by phlebotomy trained staff at the Clinical & Translational Research Center (CTRC) at UNC Memorial hospital. Patient blood samples will be obtained just prior to intravenous administration of Ca-DTPA or Zn-DTPA. IV placement will be done by nursing staff, normal saline infusion started, and Zn-DTPA injections will be done by investigator or one of the co-investigators exactly as the day prior. Five (5) minutes post injection of Zn-DTPA another blood pressure will be taken. Another 24-hour urine sample will be collected beginning after chelation therapy is initiated, to be returned then next day.

6.4 **Visit 3-** The patient will return to the hospital to drop off 24 hour urine for gadolinium testing, as well as a creatinine clearance. Blood chemistries calcium, zinc, magnesium and manganese will be evaluated, along with BUN, creatinine, sodium, potassium, chloride, phosphorus and CO₂.

6.5 **Visit 4-** The patient subject will come for a follow up assessment by a clinician 1 week (+5 days) following IV therapy, where pain and overall health assessments will be performed. If the patient lives more than 3 hours away, a phone-call follow up will be done and questionnaires will be supplied to be filled out and emailed prior to leaving the infusion therapy. The second therapy session will be scheduled for the following month.

6.6. **Visit 5-** Patient will return for 2nd round of infusion therapy to be done exactly as first, with day one of Ca-DTPA including pregnancy testing on women of child-bearing potential and pain scale assessment sheets for the week. Blood samples will be collected by phlebotomy trained staff at the Clinical & Translational Research Center (CTRC) at UNC Memorial hospital. Patient blood samples will be obtained just prior to intravenous administration of Ca-DTPA or Zn-DTPA.

6.7 **Visit 6-** Patient returns for day two of infusion therapy with Zn-DTPA. Blood samples will be collected by phlebotomy trained staff at the Clinical & Translational Research Center (CTRC) at UNC Memorial hospital. Patient blood samples will be obtained just prior to intravenous administration of Ca-DTPA or Zn-DTPA

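### Section 3.3 expects pre-chelation urine Gd to fall from the first to the third treatment, but no urine is scheduled before round 3, so as scheduled 0 of 20 subjects have the pair

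*Combined protocol and SAP*

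**What the plan says.** Section 3.3 gives two urine endpoints. One is a more than two-fold rise in 24-hour Gd after infusion. The other is: "The pre-chelation Gd amount in urine should decrease from the first to third treatment".

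The pre-treatment urine is described in three places, all before round 1:

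- Section 3.1 asks for a 24-hour collection at Visit 0 "to determine a baseline for evaluating the elimination of gadolinium before initiating the first treatment".
- Section 4.3 lists "24-hour gadolinium urine" among the screening tests.
- Section 6.1 (Visit 0) says "the patient will be instructed to collect a 24-hour urine so that gadolinium can be measured for pre-treatment values".

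The later collections are tied to the infusions. Section 6.2 (Visit 1) says "Patient will begin 24-hour urine collection once the infusion is started". Footnote a of the Time and Events Table starts them directly after therapy and is attached to all six treatment-day marks. Section 6.4 (Visit 3) says "The patient will return to the hospital to drop off 24 hour urine for gadolinium testing", and V7 and V11 follow the same pattern.

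On repetition, Section 3.1 says "The process will be repeated monthly, for a total of 3 chelation treatment time-points". Section 6.6 (Visit 5) says "Patient will return for 2nd round of infusion therapy to be done exactly as first", and Section 6.10 (Visit 9) has similar wording for the last round.

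Section 7.1 plans to look at urine Gd at baseline and following each treatment, and at the differences from baseline. Section 7.2 plans paired t-tests or Wilcoxon signed-rank tests.

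**The concern.** A first-to-third comparison of pre-chelation Gd is a within-subject contrast between two specific samples. If the second is never collected, the endpoint cannot be estimated, tested or even described, and the missing sample cannot be recovered after round 3 has begun.

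This matters more than its single sentence suggests, for two reasons. Section 1 expects the treatment to lower the body's Gd load, and this is the only stated endpoint that follows Gd over the course of treatment rather than the rise after an infusion. Section 7.1 also says the study is meant to inform the choice of endpoints for later trials, and Section 7.2 aims at effect size and variation. Without the second value the study can supply neither for this endpoint.

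There is a smaller knock-on effect on the two-fold endpoint. At rounds 2 and 3 the only available comparator is Visit 0, one and two months back, not that round's own pre-chelation level.

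**Working it through.** **Inputs.** Twenty subjects (Section 7.1); three monthly rounds, each with Ca-DTPA on day 1 and Zn-DTPA on day 2 (Sections 3.1 and 5.2); urine Gd marks from the Time and Events Table; collection start from Sections 3.1 and 6.2 and footnote a. The plan gives no power, effect size or standard deviation for this endpoint, so there is no calculation of its own to reproduce. The check is a count.

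**Step 1: class each scheduled 24-hour Gd urine.**

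| Visit | Place in schedule | Collection starts | Pre-chelation? |
|---|---|---|---|
| V0 | before round 1 | before any infusion | yes |
| V1, V2 | round 1, days 1 and 2 | with or after the infusion | no |
| V5, V6 | round 2, days 1 and 2 | with or after the infusion | no |
| V9, V10 | round 3, days 1 and 2 | with or after the infusion | no |

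Sections 3.1 and 6.2 start the collection with the treatment and footnote a starts it afterwards. None starts it beforehand. V4 and V8, the last contacts before rounds 2 and 3, have no urine Gd mark.

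Total: 1 + 6 = 7 per subject, or 20 × 7 = 140. Pre-chelation: 1 per subject.

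**Step 2: count the pairs.** Pairs = subjects × min(values before round 1, values before round 3) = 20 × min(1, 0) = **0 of 20**.

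**Step 3: try the readings that might supply a second value.**

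- *Monthly repetition in Section 3.1.* The same section ties the baseline urine to the time before the first treatment, and Section 6.1 places it at Visit 0 only.
- *Repeating the first round at V5 and V9.* This refers to the infusion round, which begins at Visit 1. Visit 0 is not repeated.
- *The void before infusion (Sections 6.2 and 6.3).* It is not a 24-hour collection, and nothing says it is kept or assayed.
- *The Labs marks at V5 and V9.* Their footnote is the pregnancy test, and urine Gd has its own row.
- *Pre/post testing in Section 7.2.* Section 7.1 fixes the time points as baseline and following each treatment, and the Table has no later pre-treatment urine.
- *The V1 urine as a sample before Zn-DTPA.* It is collected after Ca-DTPA.
- *Earlier eligibility urine (Sections 3.1 and 4.1).* It also precedes round 1.
- *Third treatment read as third infusion (V5).* No urine is scheduled before V5 either, so the count is again 0.

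**Step 4: effect on the two-fold endpoint.** Let B0 be the Visit 0 value, B3 the unmeasured level before round 3, and P3 the value after the round 3 infusion. Then P3/B0 = (P3/B3) × (B3/B0). If B3 is below B0, which is what Section 3.3 expects, the ratio to Visit 0 understates that round's own rise. Only 1 of the 3 rounds has its own pre-chelation level.

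**Step 5: after repair.**

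- One collection before V9: 20 × 8 = 160, an increase of 20/140 = 14.3%, and up to 20 pairs.
- Collections before V5 and V9: 20 × 9 = 180, an increase of 40/140 = 28.6%, and up to 20 pairs for each of first-to-second and first-to-third.

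Both assume that all 20 subjects reach the round concerned; the documents give no dropout rate.

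**The case against.** The best case on the other side accepts the count and questions its weight. This is one sentence, worded as an expectation, in a 20-subject feasibility study. No safety assessment, symptom result or round 1 two-fold result depends on it. Section 7.1 deliberately makes Visit 0 the comparator throughout, so round-specific baselines are a standard the protocol never set. The documents do not say that spontaneous urine Gd measures body load, and the six post-infusion collections do measure removal. Unscheduled visits between rounds are allowed, so a further urine could still be obtained.

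Some of this stands. The count describes the schedule as written; it does not say an extra sample is impossible. An eligibility urine may exist besides the Visit 0 one, although it too precedes round 1. The remark on the two-fold endpoint is conditional on the underlying level having fallen, and the documents give no figure for that. The link to body load is the protocol's hope, not a validated relation.

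The rest does not answer the point. The sentence stands under the heading for secondary endpoints, and a feasibility study meant to inform later endpoints has particular reason to collect the data it names. Unplanned urine from a few subjects would not be a designed comparison.

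**Conclusion.** The point holds: as written, the endpoint in Section 3.3 and the collection schedule contradict each other. The schedule supplies 1 of the 2 values needed and gives 0 of 20 evaluable pairs. The count rests on the visit descriptions and the Time and Events Table being followed as they stand, with no unscheduled 24-hour Gd urine before V9. It does not depend on any assumed rate, variance or effect. The damage is limited to this secondary endpoint, plus a conditional blurring of the two-fold ratio at rounds 2 and 3. It should be fixed before subjects reach round 3.

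**What to change.** **Preferred: keep the endpoint and collect the sample.** Add one home 24-hour Gd urine, completed before the V9 infusion, returned at V9 and marked in the Time and Events Table. Hand out the container at V7, which is a hospital visit; V8 may be a phone call for patients living more than 3 hours away (Section 3.1). A similar collection before V5, with the container given at V3, is optional and would give each round its own baseline. Section 5.5 refers only to urine after infusion, so the amendment should say whether the new collection falls under it.

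**Alternative without new samples: change the endpoint.** Use the within-patient change in post-infusion 24-hour Gd from round 1 to round 3 (V1 against V9, V2 against V10). First reconcile the collection start in Section 6.2 with footnote a, and state that this measures chelatable rather than spontaneous excretion. If neither option is wanted, the sentence should be removed from the endpoint list.

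With either of the first two, add the time point or contrast to Section 7.1. Name the paired comparison and its confidence interval in Section 7.2, under the tests already planned. State that, without a control group, a decline cannot be separated from natural washout.

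**Cost.** Preferred: one more home collection and assay per subject (7 to 8; 140 to 160 in all), or two with the optional V5 sample (9; 180 in all), and no extra visit. Alternative: no samples, but a secondary endpoint is changed. Either needs a protocol amendment submitted for IRB approval (Section 11).

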3.4 Primary Safety Endpoints

Clinically significant hypocalcemia will be monitored.

4 Subject Selection and Withdrawal

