7.1 Sample Size Determination

Twenty subjects will be evaluated to determine the safety profile of chelation in this setting and to provide information on potential endpoints for future studies in this area. The distributions of urinary measures of Gd excretion as well as for pain and quality of life will be evaluated at baseline and after each treatment, as will the differences in these measures between baseline and each treatment.

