7.2 Statistical Methods

Changes between baseline and each treatment will be evaluated for direction and magnitude. Although the goal is estimation of effect size and variation, statistical tests for changes pre/post treatment will be evaluated to understand the pre/post changes toward development of a future trial. These tests will evaluate the null hypothesis of no change in urine measures or symptoms (via questionnaire). If the changes in measures are normally distributed, then paired t-tests will be used. However, it is more likely that the data will not be normally distributed and that Wilcoxon signed-rank tests will be need. For any nominal (yes/no) questionnaire data, a McNemar's or sign test will be used for the paired contingency table. Since these tests will likely be used in future studies, direction of effect measures (differences) and ranges of estimates (confidence intervals) will provide information on what to expect in testing and analyzing more individuals

Subject Population(s) for Analysis

All-treated population: All subjects consenting to study will be treated with the same therapy, receiving at least one dose of study drug.

8 Safety and Adverse Events

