8.1 Definitions

Unanticipated Problems Involving Risk to Subjects or Others

Any incident, experience, or outcome that meets all of the following criteria:

- Unexpected in nature, severity, or frequency (i.e. not described in study-related documents such as the IRB-approved protocol or consent form, the investigators brochure, etc)
- Related or possibly related to participation in the research (i.e. possibly related means there is a reasonable possibility that the incident experience, or outcome may have been caused by the procedures involved in the research,

- Serious (as defined below) “**Serious**” is different than “severe” as reported in the CTC criteria that applies a grade to the AE.

Adverse Event

An **adverse event** (AE) is any symptom, sign, illness or experience that develops or worsens in severity during the course of the study. Intercurrent illnesses or injuries should be regarded as adverse events. Abnormal results of diagnostic procedures are considered to be adverse events if the abnormality:

- results in study withdrawal
- is associated with a serious adverse event
- is associated with clinical signs or symptoms
- leads to additional treatment or to further diagnostic tests
- is considered by the investigator to be of clinical significance

Serious Adverse Event

Adverse events are classified as serious or non-serious. A **serious adverse event** is any AE that is:

- fatal
- life-threatening
- requires or prolongs hospital stay
- results in persistent or significant disability or incapacity
- a congenital anomaly or birth defect
- an important medical event

Important medical events are those that may not be immediately life threatening, but are clearly of major clinical significance. They may jeopardize the subject, and may require intervention to prevent one of the other serious outcomes noted above. For example, drug overdose or abuse, a seizure that did not result in in-patient hospitalization or intensive treatment of bronchospasm in an emergency department would typically be considered serious.

All adverse events that do not meet any of the criteria for serious should be regarded as **non-serious adverse events**.

For the purpose of this trial, the following will be considered expected adverse events:

Ca-DTPA—headache, lightheadedness, chest pain, allergic reaction, dermatitis, metallic taste, nausea and diarrhea, and injection site reactions.

Zn-DTPA—headache, lightheadedness, and pelvic pain.

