Possible “flare effect”, resulting in exacerbation of current symptoms.

Adverse Event Reporting Period

The study period during which adverse events must be reported is normally defined as the period from the initiation of any study procedures to the end of the study treatment follow-up. For this study, the study treatment follow-up is defined as 30 days following the last administration of study treatment.

Preexisting Condition

A preexisting condition is one that is present at the start of the study. A preexisting condition should be recorded as an adverse event if the frequency, intensity, or the character of the condition worsens during the study period.

General Physical Examination Findings

At screening, any clinically significant abnormality should be recorded as a preexisting condition. At the end of the study, any new clinically significant findings/abnormalities that meet the definition of an adverse event must also be recorded and documented as an adverse event.

Post-study Adverse Event

All unresolved adverse events should be followed by the investigator until the events are resolved, the subject is lost to follow-up, or the adverse event is otherwise explained. At the last scheduled visit, the investigator should instruct each subject to report any subsequent event(s) that the subject, or the subject's personal physician, believes might reasonably be related to participation in this study. The investigator should notify the study sponsor of any death or adverse event occurring at any time after a subject has discontinued or terminated study participation that may reasonably be related to this study. The sponsor should also be notified if the investigator should become aware of the development of cancer or of a congenital anomaly in a subsequently conceived offspring of a subject that has participated in this study.

Abnormal Laboratory Values

A clinical laboratory abnormality should be documented as an adverse event if any one of the following conditions is met:

- The laboratory abnormality is not otherwise refuted by a repeat test to confirm the abnormality
- The abnormality suggests a disease and/or organ toxicity
- The abnormality is of a degree that requires active management; e.g. change of dose, discontinuation of the drug, more frequent follow-up assessments, further diagnostic investigation, etc.

Hospitalization, Prolonged Hospitalization or Surgery

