8.4 Stopping Rules

The study will be stopped for review if there is greater than 2 of the first 3 patients, or 5 of the first 10 patients experience an unanticipated severe adverse event, or more than one grade IV expected adverse events as defined by CTCAE v.4.0.

Study subjects will be withdrawn from the study if they experience any unknown severe adverse event (grade 3 or 4) following administration of either Ca-DTPA or Zn-DTPA. We will be using the CTCAE v.4.0 scale to measure severity of adverse events.

Any patient who shows a Grade 3 hypocalcemia (<7.0-6.0 mg/dl) post infusion therapy will be discontinued from the study.

The study will be stopped for any study-related death.

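### The primary safety endpoint, clinically significant hypocalcemia, has no operational criterion, and the paired calcium values collected for every round have no planned analysis

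*Combined protocol and SAP*

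**What the plan says.** **The endpoint.** Section 3.4 reads, in full: "Clinically significant hypocalcemia will be monitored". It gives no cut-off, time window, assessor or summary measure.

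**Rules elsewhere that touch a low calcium value.**
- Section 8.1, adverse event definition: an abnormal test result is an adverse event if it meets one of five conditions. The last is that it "is considered by the investigator to be of clinical significance".
- Section 8.1, Abnormal Laboratory Values: any one of three conditions is enough. The first is: "The laboratory abnormality is not otherwise refuted by a repeat test to confirm the abnormality".
- Section 8.4: "Any patient who shows a Grade 3 hypocalcemia (<7.0-6.0 mg/dl) post infusion therapy will be discontinued from the study". This is the only calcium figure in the document. The same section adds: "We will be using the CTCAE v.4.0 scale to measure severity of adverse events".

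**The analysis.** Section 7.1 ties the sample size to safety: "Twenty subjects will be evaluated to determine the safety profile of chelation in this setting". The measures it then lists are others: "The distributions of urinary measures of Gd excretion as well as for pain and quality of life will be evaluated at baseline". Section 7.2 says of its pre/post tests: "These tests will evaluate the null hypothesis of no change in urine measures or symptoms (via questionnaire"). Calcium is in neither list. For safety, 8.5 says only that adverse events will be recorded and summarized for the manuscript.

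**The data.** Calcium is among the screening chemistries (4.3) and is measured again at Visits 3, 7 and 11 (6.4, 6.8, 6.12), the day after each round's Zn-DTPA infusion.

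**The concern.** An endpoint needs a rule that turns a measured value into an event or a non-event, and 3.4 has none. The reader has to borrow one from 8.1 or 8.4, and those rules serve other purposes and do not agree. The primary safety count could then differ on identical calcium values, with the choice made after the values are known.

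The second part matters more for what the study can conclude. Section 7.2 says its goal is to estimate effect size and variation, and 7.1 puts the safety profile first among the reasons for 20 subjects. Yet the laboratory variable behind the named safety endpoint is not among the measures to be described or tested. Paired values will exist for each round with no plan to use them. A count of rare events in 20 patients is a weak instrument for a shift that affects most patients modestly; the paired change from the same samples is a much sharper one.

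**Working it through.** **1. One value under each rule.** Take a post-infusion calcium of 7.8 mg/dl. Assume it is below the laboratory's reference range, which the document does not give.

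| Rule | Classification of 7.8 mg/dl |
|---|---|
| 3.4, primary safety endpoint | Cannot be determined |
| 8.1, adverse event definition | Event only if one of five conditions holds; with no symptoms, further action, withdrawal or associated serious event, it rests on the investigator's view |
| 8.1, Abnormal Laboratory Values | Event if a repeat test does not refute it; that view is not needed |
| 8.4, grade 3 | Not met, since 7.8 is above 7.0 |

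No passage says which row feeds 3.4. A fall from, say, 9.8 to 9.0 mg/dl, if both values are in range, would not be an abnormal result under any row.

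**2. Is there a plan figure to reproduce?** No. N = 20 comes without an event rate, SD or power. What follows is illustration. Only n = 20, the 7.0 mg/dl boundary and the 0.05 significance level are from the document. Two-sided testing and all calcium means, falls and SDs are assumptions.

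**3. Precision of the paired change.** Half-width = t(0.975, 19) × SD/√20, with t = 2.093. Power for a mean fall of 0.3 mg/dl comes from the noncentral t with noncentrality 0.3/(SD/√20).

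| SD of change (mg/dl) | 95% CI half-width (mg/dl) | Noncentrality | Power, fall of 0.3 |
|---|---|---|---|
| 0.3 | 0.14 | 4.47 | 99% |
| 0.4 | 0.19 | 3.35 | 89% |
| 0.5 | 0.23 | 2.68 | 72% |
| 0.6 | 0.28 | 2.24 | 56% |

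**4. Information in a zero count.** The exact two-sided 95% upper limit for 0/20 is 1 − 0.025^(1/20) = 16.8%.

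**5. How often would a fall produce a value below 7.0?** Assume baseline mean 9.4 and SD 0.4, change independent of baseline, and one post-treatment value per patient. Then p = Φ((7.0 − (9.4 − fall))/√(0.4² + SD²)), and the chance of at least one such patient is 1 − (1 − p)^20. For example, with a fall of 0.5 and SD of change 0.5: (7.0 − 8.9)/0.640 = −2.97, p = 0.0015, and 1 − 0.9985^20 = 3%.

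| Mean fall (mg/dl) | SD 0.3 | SD 0.5 | SD 0.7 |
|---|---|---|---|
| 0.5 | 0.1% | 3% | 17% |
| 1.0 | 5% | 25% | 57% |
| 1.5 | 52% | 81% | 94% |

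For the 0.5 fall, paired-test power at the same three SDs is over 99%, 99% and 86%. If the three rounds are treated as 60 independent values, the first row becomes 0.4%, 9% and 43%. A moderate fall can thus be clear in the paired data and leave no grade 3 value; for large falls the two measures agree.

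**The case against.** The strongest reply is that the protocol does not let low calcium disappear. The laboratory rule in 8.1 records an abnormality that repeat testing has not refuted, whatever the investigator thinks of its significance, and 8.5 has all adverse events summarized. CTCAE v4.0 is adopted for severity, and a safety monitor who is not an investigator reviews the case report forms after subjects 1, 3, 10 and 20. All of this stands. It limits the consequence to the 3.4 count itself and to falls that stay in range. It does not say what counts towards 3.4 or supply an analysis of the calcium values.

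Three stronger readings are tempting and should be resisted.
- A reader might infer that 3.4 makes the endpoint a matter of investigator judgement. It does not say so; judgement is one of five alternatives in a general definition in 8.1.
- A reader might infer that grade 3 is the endpoint and that its count is bound to be 0/20. Section 8.4 uses grade 3 only to discontinue an individual patient, and step 5 shows that zero is not assured: for a 1.0 mg/dl fall, the chance of at least one value below 7.0 is 25% to 57% at SDs of change of 0.5 to 0.7.
- A reader might infer that mean change should replace the event endpoint. The stated endpoint concerns clinical harm. A mean fall of 0.3 to 0.5 from an assumed 9.4 leaves a mean of 8.9 to 9.1, and few clinically significant events could then be the right answer. The defect calls for adding the change, not for substituting it.

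It is also fair to say that this is a small feasibility study. But since 7.2 makes estimation the goal, that argues for estimating the calcium change.

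**Conclusion.** The point holds in this form. The primary safety endpoint lacks an operational criterion, the rules in 8.1 and 8.4 can classify one calcium value differently without any of them being tied to 3.4, and the paired calcium data have no planned analysis. These conclusions rest on the text alone.

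The consequence is limited: a consistent fall can go unseen in the 3.4 count, particularly one within the normal range. The documents do not support saying that such a fall would be missing from safety reporting altogether.

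The size of the gain depends on calcium variability, which the document does not give. Over the assumed SDs in step 3, the paired interval is narrow enough to be useful throughout, but power for a 0.3 mg/dl fall ranges from high to little better than even. The change is worth making because it costs almost nothing and improves what the study can say about its named safety endpoint.

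**What to change.** 1. **Section 3.4.** Keep the hypocalcemia event endpoint and state which recorded events count towards it, including the time window and who decides. The choice of criterion is the sponsor's.
2. **Sections 3.4, 8.1 and 8.4.** Reconcile the endpoint with the adverse event definition, the laboratory-abnormality rule and the grade 3 rule, so that each calcium value has one classification for each purpose. The discontinuation rule in 8.4 is not changed by this.
3. **Sections 7.1 and 7.2.** Add serum calcium to the listed measures. Report the paired change from screening to Visits 3, 7 and 11 with 95% CIs, each patient's lowest measured value, and the number of patients at each CTCAE v4.0 hypocalcemia grade with exact 95% CIs.

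**Cost.** Wording in these sections and one additional table. No new samples or visits are needed, because calcium is already measured at all four time points.
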